8.0 ADVERSE EVENTS: LIST AND REPORTING REQUIREMENTS

8.1 ADVERSE EVENT REPORTING

Subject data accrued on this study will be reported in accordance with Code of Federal Regulations Title 21 (21CFR) 312.32.

This study will utilize the descriptions and grading scales found in the revised NCI Common Terminology Criteria for Adverse Events (CTCAE) version 4.03 for grading all adverse events. All appropriate treatment areas should have access to a copy of the CTCAE version 4.03. A copy of the CTCAE version 4.03 can be downloaded from the CTEP web site (<http://ctep.cancer.gov>).

8.1.1 The P.I. will notify the DSMC, IRB, the FDA and other regulatory agencies of all serious adverse events as required by law or regulation.

8.1.2 Serious Adverse Event (AE) Reporting by investigators will be done as outlined in Table 2.

8.1.3 Definitions for reporting purposes:

Associated with the use of the drug: There is a reasonable possibility that the AE was caused by the drug. (attributions of possible, probable or definite)

Attribution: The determination of whether an AE is related to medical treatment or procedure.

Attribution Categories:

Attribution	Description
Unrelated	The AE is clearly NOT related to the intervention.
Unlikely	The AE is doubtfully related to the intervention.
Possible	The AE may be related to the intervention.
Probable	The AE is likely related to the intervention.
Definite	The AE is clearly related to the intervention.

Reporting Form and Content: For those events that meet the criteria in Table 2, please complete the Serious Adverse Event Reporting Form (MedWatch 3500a Form).

8.1.4 Follow-up information:

Additional information may be added to a previously submitted report by any of the following methods:

- Adding to the original MedWatch 3500a report and submitting it as follow-up
- Adding supplemental summary information and submitting it as follow-up with the original MedWatch 3500a form
- Summarizing new information and faxing it with a cover letter including subject identifiers (i.e. D.O.B. initial, subject number), protocol description and number, if assigned, suspect drug, brief adverse event description, and notation that additional or follow-up information is being submitted

(The subject identifiers are important so that the new information is added to the correct initial report)

- In addition to sending the MedWatch 3500a form to the FDA, it will be submitted to the DSMC through the CRSO and the IRB if serious and related to the study drugs.

8.1.5 IRB Reporting of Serious Adverse Events and Deaths

The Protocol PI will report to the IRB all serious adverse events that are possibly, probably or definitely related to the research, as well as other reportable events, in accordance with the reporting guidelines of the IRB.

8.2 ROUTINE ADVERSE EVENT REPORTING

All Adverse Events must be reported in routine study data submissions. AEs reported through expedited SAE reports must also be reported in routine study data submissions (eCRFs).

8.3 REPORTING REQUIREMENTS FOR BASELINE ADVERSE EVENTS

Positive findings identified on baseline assessment are to be documented as a Baseline Adverse Event using CTCAE terminology and grade on the provided Baseline CRF. An expedited AE report is not required if a patient is entered on to the study with a pre-existing condition (e.g., elevated laboratory value, diarrhea). The baseline AE must be re-assessed throughout the trial and reported if it fulfills expedited AE reporting guidelines.

- If the pre-existing condition worsens in severity, the investigator must reassess the event to determine if an expedited report is required.
- If the AE resolved and then recurs, the investigator must re-assess the event to determine if an expedited report is required.
- No modification in grading is to be made to account for abnormalities existing at baseline.

8.4 ADVERSE EVENT CASE REPORT FORM

[figure not shown]
All adverse events (regardless of grade and attribution) observed while on study and for 30 days after last dose of treatment, must be recorded on the adverse event case report form in OnCore. After 30 days from last dose of treatment, only adverse events that are attributed to the study drug (possible, probable, or definite) are required to be recorded on the adverse event forms. Reporting of adverse events after 30 days from the last dose of treatment should be completed as written in Table 1.

9.0 PHARMACEUTICAL INFORMATION

9.1 SLM

Chemical Name: L-selenomethionine

Chemical Structure:

Molecular weight: 196.11 g/mol

Molecular and structural formula: C5H11NO2Se

CAS Registry Number: 3211-76-5

How supplied: Sabinsa Corporation, NJ, USA

Route of Administration: Oral

Storage: Investigational Drug will be stored in the Investigational Pharmacy at University of Iowa Hospitals and Clinics

Pharmacokinetics of L-Selenomethionine (SLM) in humans

Fakih et al conducted a phase I study to determine the dose of SLM in combination with Irinotecan required to achieve a plasma Se concentration greater than 15 μ M after 1 week of loading (5). SLM was administered orally, twice a day for the first 7 days followed by a daily maintenance dose. Doses were escalated as per Table 2 and trough Se blood levels were sampled on days 1, 2, 8 and 28.

Phase I escalation schema			
Dose level	SLM loading (D-7–D-1) ^a (mcg PO BID)	SLM maintenance (D1 and on) (mcg PO QD)	Irinotecan (mg/m ²) Q week (start on D1)
1	3,200	2,800	125
2	3,200	3,200	125
3	4,000	3,200	125
4	4,000	4,000	125
5	4,800	4,800	125
6	5,600	5,600	125
7	7,200	7,200	125

Table 2. Dosing schema from SLM study by Fakih et al

Table 3 shows Se plasma levels on days 8 and 28 in patients from all dose cohorts. While there was significant inter-patient variability in Se levels at day 8, all patients from dose level 5 upwards achieved the target 15 μ M or more. There was no significant further accumulation of Se observed at day 28 until dose level 7. Serum Se levels were measured every 6 weeks in patients who remained on study for more than 1 cycle (median number of cycles 2 (range 1-8)), a plateau was reached at or around the levels achieved on day 28.

Toxicity of SLM in humans

In the Fakih study with SLM given in combination with Irinotecan, SLM was observed to be well-tolerated in all patients, with attributable toxicity limited to mild garlic-like odor in breath and urine in about 50% of the patients (5). This was seen more commonly during the induction SLM week and tended to ameliorate or disappear with prolonged treatment. No skin or nail toxicities secondary to SLM were documented. The non-tolerable dose of SLM was not defined in this study but the highest dose level administered (7200 μ g twice a day for 1 week followed by 7200 μ g daily) was deemed to be the MTD because 1 of 6 patients developed grade 3 infection, neutropenia, diarrhea, and hyponatremia.

Plasma concentrations of axitinib may be altered by the concomitant use of drugs that affect the cytochrome P450 isoenzymes CYP3A4 and CYP3A5. Strong inhibitors of these enzymes should be avoided, but if they must be used then the dose of axitinib should be reduced. Grapefruit and grapefruit juice should also be avoided. Moderate and strong inducers of these enzymes can reduce axitinib concentrations and should therefore be avoided during axitinib therapy.

Toxicities of axitinib

- The most common adverse effects of axitinib include gastrointestinal disturbances, reduced appetite, weight loss, fatigue, asthenia, dysphonia, and palmar-plantar erythrodysesthesia.
- Hypertension is also common and cases of hypertensive crisis have been reported. Blood pressure should be well-controlled before starting axitinib and monitored during therapy. Antihypertensive treatment may be needed but the dose of axitinib should be reduced if hypertension persists; axitinib should be stopped if hypertension is severe and persistent or there is evidence of hypertensive crisis. Arterial and venous thromboembolism have occurred in patients given axitinib. Reported hemorrhagic events have included cerebral hemorrhage, hematuria, and gastrointestinal bleeding. Gastrointestinal perforation and fistula formation have also been reported.
- Other adverse effects include thyroid dysfunction, proteinuria, and elevations of liver enzymes values; patients should be assessed for these before starting axitinib and monitored during therapy. There have also been cases of reversible posterior leukoencephalopathy syndrome in patients given axitinib.
- Axitinib should be stopped at least 24 hours before surgery, because of potential impairment of wound healing. (Last reviewed: 2012-03-05; last modified: 2012-03-26)

10.0 BIOMARKER AND CORRELATIVE STUDIES

10.1 BIOMARKER STUDIES:

As SLM is supposed to inhibit the expression of hypoxia inducible factors (HIF) in tumor cells, there is a possibility that downstream expression of vascular endothelial growth factors (VEGF) would be affected, thereby tumor vasculatures will be normalized and will have less leaky vessels (less permeability). Three specific markers are proposed to look at before and after treatments: **(1) HIF- α 1, (2) HIF- α 2, and (3) VEGF-A.**

Blood and tissue will also be collected for the determination of **miRNA** 210, 155, and Let-7b related to the disease process.

Escalation Subjects: COMPLETED on 10/23/18

SLM blood levels will be measured at baseline, on day 14, at cycles 2, 3, 4, 5, 6, and 7 then at cycles 10, 13 and 16 to correlate between blood levels and the effect on HIF-a expression. Extra blood sample of 20 ml will be collected in un-heparinized tubes, spin and stored at -80c for other biomarkers that might be added later on.

Expansion Subjects:

SLM blood levels will be measured at baseline pre dose and 2 hours post dosing, then 2 hours post dosing on day 14, at cycles 2, 3, 4 7 then at cycles 10and 13to correlate between blood levels and the effect on HIF-a expression. Extra blood sample of 20 ml will be collected in un-heparinized tubes, spin and stored at -80c for other biomarkers that might be added later on.

10.2 ARCHIVAL TUMOR TISSUE AND BIOPSY:

Archival Tumor Tissue:

A sample of archival tumor tissue, if available will be obtained for a select number of patients enrolled in the dose escalation and expansion portions of the study for biomarker studies.

Mandatory Fresh Biopsy:

Tumor biopsies should be obtained according to standard institutional procedures. The biopsies are preferred to be collected from the same lesion and the same location within the lesion at each visit of sampling. Obtain enough tissue to generate a minimum of 3 biopsy samples; one to be processed to an FFPE block for IHC, one to be processed for miRNA isolation, and one to be snap frozen for any downstream correlative testing deemed necessary. Biopsies will be obtained from Interventional Radiology and processed for research by the Tissue Procurement Core according to standard operating procedure.

For Formalin Fixation – Wrap one of the biopsy samples in Biowrap and place in a pre-labelled cassette. Place the entire cassette containing the biopsy immediately into a specimen container filled with 10% neutral buffered formalin (NBF). Transfer the specimen container containing the biopsy and cassette to surgical pathology to be processed and for embedding in paraffin according to standard institutional guidelines. Store the block at ambient temperature until testing. The biopsy should go from patient to formalin in the minimum amount of time

possible, but not to exceed 10 minutes. The formalin fixation time should be at least 6 hours, not to exceed 72 hours.

For RNAlater – Place one of the biopsy samples in a cryovial containing RNAlater solution immediately. Store the biopsy in RNAlater overnight at 4°C. The following morning, remove the supernatant and move the biopsy sample to -80°C to store until testing. The biopsy should go from patient to RNAlater solution in the minimum amount of time possible, but not to exceed 10 minutes.

For Flash Frozen – Place one of the biopsy samples in an RNase-free cryovial. Freeze in the vapor phase of LN2 immediately without submerging the tissue. Store the biopsy in LN2 vapor until testing. The biopsy should go from patient to frozen in the minimum amount of time possible, but not to exceed 10 minutes.

11.0 STUDY CALENDAR - SLM + AXITINIB FOR CLEAR CELL RCC

Evaluation	Screening Day ² -28 prior to Day 0				SLM Run-in Phase (+/- 2 days)				Cycle 1 (+/- 3 days)				Cycle 2 and subsequent cycles (+/- 3 days) ¹⁶				End of Treatment (28 days +/- 7 days) after last dose	Follow-up occurring approximately every 6 months
	Week 1	Week 2	Week 1	Week 2	Week 3	Week 4	Week 1	Week 2	Week 3	Week 4	Week 2	Week 3 ⁶	Week 4	Week 2	Week 3 ⁶	Week 4		
Informed consent	X																	
Verify eligibility criteria	X																	
Medical History ¹	X				X													
Concurrent medication	X				X													
Vital signs	X				X													X
Physical exam ¹	X				X													X
Performance status evaluation	X				X													X
ECG	X																	
Lipid Panel	X																	
CBC w/diff	X				X													X
ALT, AST, Alk phos, T.bili Na, K, calcium, magnesium, BUN, creatinine, T. protein, albumin, LDH	X				X													X
Erythropoietin, serum	X																	
Urinalysis	X				X	Day 14												X
Pregnancy test for WOCCBP	X				X													X
PT/INR, PTT	X																	
Glucose	X																	X
miRNA (blood draw) ⁸			Day 1	Day 14														
Fresh Tumor Tissue biopsy			Day 1	Day 14														
IHC (up to 20 patients in expansion phase and pilot phase) ¹³																		
SLM Concentration ⁸			X ⁸	X ⁸														
Archival tumor tissue			X ⁸	X ⁸														
Additional blood for storage ⁸			X ⁸	X ⁸														

CT +/- Bone scan ³				Beginning at Cycle 5 Day 1 Imaging will be repeated every 8 weeks +/- 5 days. ^{14,17}
CT +/- Bone scan ³	X ⁷			Scans will be repeated every 8 weeks +/- 5 days, starting 8 weeks after first dose of SLM plus Axitinib, as clinically indicated. ¹⁷
Escalation Phase				
Dual Energy CT ¹⁵	X ⁷	Day 14		8 weeks after first dose of SLM plus Axitinib (Cycle 3)
Expansion/Pilot Phase				
SLM Dosing				
Axitinib Dosing				
Adverse Event Assessment				
Safety Phone Call		X	X	X ¹¹

¹ History and physical exam will be performed by physician and/or midlevel provider or designated fellow. To include cardiac risk factors, smoking history, family history of cardiac disease, use of aspirin.

² Events may be performed Day 1 of SLM run-in if resulted/reviewed prior to dosing.

³ CT scan (with or without Contrast) of chest, abdomen and pelvis with or without bone scan based on provider's judgment. Bone Scans will only be repeated if lesion is present at baseline.

⁵ These labs will be drawn as clinically indicated.

⁶ Visit 3 for Cycle 2 and beyond will only occur if clinically indicated.

⁷ Screening CT to be performed within 28 days from SLM Day 1.

⁸ See Table 20.0 for Escalation patients. See Table 20.1 for Expansion patients. See Table 20.2 for Pilot Phase patients.

⁹ Cycle 3 only

¹⁰ Blood drawn for glucose testing every even cycle beginning with Cycle 2.

¹¹ Patients will be followed up, until they are lost to follow-up or death, whichever occurs first. Patients removed from study for unacceptable adverse event(s) will be followed for resolution or stabilization of the adverse event as well. Follow up off study will be performed using telephone contact, correspondence with treating physicians, and death records as necessary to update vital status at least every 6 months.

¹² Archival tumor tissue will be obtained, if available and if subject agrees.

¹³ Fresh research tissue biopsies will occur in up to 20 subjects enrolled into the Expansion Phase and pilot phase, that the PI deems as safe and tumor is accessible. An additional fresh research tissue biopsy may occur at progression for subjects that the PI deems as safe and tumor is accessible.

¹⁴ CT +/- Bone scans will be performed as clinically indicated beginning at Cycle 5, Day 1. Prior to Cycle 5, Day 1 Dual Energy CT's will be performed.

¹⁵ For subjects in expansion phase and pilot only Dual Energy CT's will follow protocol as outlined in Section 22.

¹⁶ Per PI or Sub-J discretion, subjects may be seen at odd cycles after Cycle 11 is completed (Cycle 11, 13, 15, 17, etc). Subjects who are allowed to be seen at odd cycles will be dispensed with 8 weeks of study drug and asked to contact the research team with any issues or concerns between visits. (if patient is seen at odd cycles then no assessments are required at even cycles. Labs may be obtained locally.)
¹⁷ If subject is asymptomatic, bone scans may be done every 4 months.

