3.0 PATIENT SELECTION

3.1 ELIGIBILITY CRITERIA

Each patient must meet all of the following criteria to be enrolled in this study:

1. Histologically and radiologically confirmed advanced metastatic CCRCC in patients who have had at least one prior systemic therapy, which can include axitinib for the dose escalation part. In the expansion and pilot phases, patients with prior axitinib are allowed, as long as the last dose of axitinib was longer than 6 months ago.
2. Written and voluntary informed consent.
3. At least one Response Evaluation Criteria In Solid Tumors (RECIST)-defined target lesion.
*Patient must have documented disease progression.
4. Renal function (creatinine level within normal institutional limit, or creatinine clearance >15 mL/min/1.73 m² for patients with creatinine levels above institutional normal, calculated using the Cockcroft-Gault formula).
5. Liver function (AST/ALT ≤ 2.5 X institutional upper limit of normal **OR** ≤ 5 x institutional upper limit of normal in cases of liver metastases; Total bilirubin ≤ 1.5 times ULN.)
6. Adequate hematological lab values including:
 - Absolute Neutrophil Count (ANC) $\geq 1.0 \times 10^9/L$
 - Platelets $\geq 100 \times 10^9/L$
 - Hemoglobin ≥ 7.0 g/dL
7. Eastern Cooperative Oncology Group (ECOG) performance status of 0 (fully active, able to carry on all pre-disease performance without restriction), 1 (restricted in physically strenuous activity but ambulatory and able to carry out work of a light or sedentary nature, such as light housework or office work) or 2 (Ambulatory and capable of all self-care but unable to carry out any work activities; up and about more than 50% of waking hours).
8. Age of at least 18 years.
9. Life expectancy of 12 weeks and more.
10. 2 weeks or more since end of previous systemic treatment (4 weeks or more for bevacizumab plus interferon-alfa). 3 days wash out for palliative radiation.
11. Must have a safely accessible biopsy per treating physician and the provider performing that biopsy. Patient must agree to have this biopsy done as outlined in the calendar. If patient does not have safely accessible biopsy, the patient may still be enrolled per investigator discretion.

3.2 EXCLUSION CRITERIA:

Patients eligible for this study must not meet any of the following criteria:

1. Patients with prior malignancies of the same or different tumor type in the last 5 years and patients with

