4.1.1 Consent Process

Subjects will be consented by a member of the study team after receiving an explanation of the study, review of the consent form, and having had all questions answered by a member of the study team. . The subject will be provided with a copy of the signed consent form.

An automatic notification will be sent to appropriate staff, including the safety officer after consent, following entry of patient information into the clinical trials management system (OnCore).

4.1.2 Eligibility Assessment:

Eligibility will be assessed according to the protocol. An eligibility check list will be completed and signed by the treating physician, documenting his/her review of all eligibility criteria and confirming all screening assessments have been completed and the subject meets criteria to begin protocol treatment. Once eligibility is confirmed by the treating physician, a signed copy of the eligibility checklist will be scanned and entered into OnCore and automatic notifications sent to appropriate staff.

Disease assessment is to be performed within the 28 days prior to the start of study treatment using CT scan of chest, abdomen and pelvis with or without bone scan based on provider's judgment. Patient disease assessment will be performed according to RECIST 1.1 criteria for solid tumors.

The following pre-treatment evaluations are to be performed within 28 days prior to the start of treatment:

- Compliance with eligibility criteria
- Patient demography
- Medical history (to include a complete history of previous, present and concomitant conditions and treatment)
- Physical examination (complete physical examination, including height, weight and BSA)
- Vital signs (to include blood pressure, heart rate, respiratory rate, and body temperature)
- Assessment of ECOG performance status
- CBC with differential to include: hemoglobin, differential white blood cell count, platelet count. Coagulation parameters including INR (International Normalized Ratio), aPTT, and PT.

- Clinical chemistries to include: ALT, AST, total bilirubin, sodium, potassium, calcium, magnesium, urea, creatinine (creatinine clearance calculated using the Cockcroft and Gault formula), total protein, albumin, LDH, Alkaline phosphate.
- Urinalysis
- Glucose
- Erythropoietin per calendar
- Assessment of cardiac risk factors (Lipid profile, smoking, family history of cardiac disease, use of aspirin)
- Concomitant medications
- 12-Lead ECG after 5 minutes supine rest.

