- Pregnancy test (this test is mandatory in women of child-bearing potential)
- Dual Energy CT Scan – Expansion and pilot Phases Only

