21.2 CT PROTOCOL

The same CT scan protocol will be obtained at 3 time points;

- Visit 1: baseline prior to treatment
- Visit 2: 14 ± 2 days following start of SLM
- Visit 3: 56 ± 3 days following start of chemotherapy (axitinib)

If for any reason baseline DECT could not be performed, we will utilize only regular CT scan subsequently in that setting (cancel further DECT) and there will NOT be a need for day 14 scan. This need to be discussed by PI before enrollment on study.

21.3 DUAL ENERGY CT:

- Contrast: 50% saline mixed with 50% 370mg/ml Iopamidol delivered at 4ml/s (4ml/s (35 s+ 5s) = 160ml of which 80ml is contrast) with delay of 35s (for chest) and 70s (for abdomen/pelvis)
- Positioning: Cranialcaudal acquisition with scan coverage (DFOV) from pubic symphysis to apex of lungs (DFOV to match prior visit). Acquisition at coached total lung capacity (TLC) (recorded for DECT)
- Acquisition: CHEST: The spiral DECT contrast scan with dose modulation with tube A: 120 ref mAs/80kV, tube B: 67 ref mAs/Sn150 kV, with a pitch of 0.55 and rotation time of 0.25sec. The CTDIvol is assumed to be 4.28mGy, with total DLP of 143.2mGy*cm for a 30cm scan.
- Acquisition: ABDOMEN: The spiral dual energy contrast abdomen/pelvis scan protocol uses dose modulation with tube A: 190 ref mAs/100kV, tube B: 95 ref mAs/Sn150 kV, with a pitch of 0.55 and rotation time of 0.25sec. The CTDIvol is assumed to be 10.41mGy, with total DLP of 553.7mGy*cm for a 50cm scan.
- Reconstruction: R1: 0.75 x0.5; R2: 2.0 x 1.4, Qr40(Admire 5), FOV to match prior visits, Energy Series: A, B and M. Keep Raw data.

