21.4 ANALYSIS

- Hypothesis: SLM will improve vascularization of tumors (ie increase in tumor iodine density at visit 2) which will allow for more effective chemotherapy treatment (ie decrease in tumor iodine density at visit 3, and decrease in tumor size). Secondary analysis may examine if baseline (visit 1) levels correlate with SLM response and/or treatment outcome (ie tumors with poor vascularization at visit 1, benefit more from SLM).

- Syngo via (initial analysis on 2.0x 1.4 recon) to produce virtual non-contrast image (VNC), mono energetic 40keV, Iodine concentration PBV (HU and mg/ml)
- Examine analysis results using fixed region of interest (ROI) in tumor volume vs semi-automatic tumor segmentation.

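### After a prior VEGF-targeted TKI other than axitinib, the baseline dual-energy CT may precede that drug's last dose by up to 14 days, so a rise in iodine density at visit 2 cannot be credited to SLM alone

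*Combined protocol and SAP*

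**What the plan says.** Two timing rules apply before SLM Day 1.

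- **Scan window.** Section 4.1.2 states: "Disease assessment is to be performed within the 28 days prior to the start of study treatment". Its list of evaluations opens with "The following pre-treatment evaluations are to be performed within 28 days prior to the start of treatment" and ends with "Dual Energy CT Scan – Expansion and pilot Phases Only". Footnote 7 of the calendar (Section 11.0) repeats the limit, "Screening CT to be performed within 28 days from SLM Day 1", and marks the dual-energy CT row.
- **Washout.** Section 3.1, item 10 requires "2 weeks or more since end of previous systemic treatment (4 weeks or more for bevacizumab plus interferon-alfa"). Item 1 separately requires, in the expansion and pilot phases, that any prior axitinib ended more than 6 months earlier.

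Section 21.2 defines the first dual-energy scan only as "Visit 1: baseline prior to treatment" and places the second at day 14 ± 2 of SLM, the end of the SLM-only run-in. Section 21.4 states the hypothesis to be read from these two scans: "SLM will improve vascularization of tumors (ie increase in tumor iodine density at visit 2"). It then expects iodine density to fall at visit 3, after axitinib. Section 14.5 confirms that nothing is randomized. Section 21.4 plans no adjustment for time since the previous therapy.

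**The concern.** The visit 1 to visit 2 comparison is meant to isolate what SLM does to tumor vascularity before axitinib has had time to act. That works only if nothing else changes between the scans. The scan window is longer than the general washout, and no section ties the baseline scan to the last dose of the previous drug. A patient can therefore be scanned while still taking an anti-angiogenic TKI, stop it, start SLM and be scanned again.

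The plan itself expects iodine density to fall under axitinib, a VEGF-receptor inhibitor (Section 2.5). By the same logic, stopping a drug of that class could let it rise, which is the direction credited to SLM. Without a control group, the two explanations cannot be separated in such a patient. At stake is whether a positive visit 2 finding could be used as evidence that SLM alters tumor vasculature.

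**Working it through.** The plan states no figure for this point, so there is none to reproduce. The check is interval arithmetic.

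**Inputs, in days relative to SLM Day 1**

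- Scan window W = 28 (footnote 7; Section 4.1.2).
- Minimum gap since prior therapy G = 14 in general and 28 for bevacizumab plus interferon-alfa (Section 3.1, item 10). For prior axitinib in the phases that have dual-energy CT, G is about 182, taking 6 months as 182 days (item 1).
- Visit 2 at V = 14 ± 2, that is 12 to 16 (Section 21.2).
- Assumption: the washout is counted to SLM Day 1, because item 10 does not name its end date. Section 4.1.2 has eligibility signed off once the screening assessments are complete, which is consistent with a washout that ends after the scan.

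**Formulas**

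- Longest time by which the scan can precede the last prior dose = max(0, W − G).
- Time off the prior drug at visit 2, for a patient with the minimum gap = G + V.

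| Last prior therapy | Scan before last dose, at most | Off drug at visit 2, minimum gap |
|---|---|---|
| Other systemic therapy, including sunitinib, sorafenib, pazopanib | 28 − 14 = 14 days | 14 + 12 = 26 to 14 + 16 = 30 days |
| Bevacizumab plus interferon-alfa | 28 − 28 = 0 days | 28 + 12 = 40 to 28 + 16 = 44 days |
| Axitinib (expansion, pilot) | 0 days; at least 182 − 28 = 154 days off drug | 182 + 12 = 194 to 182 + 16 = 198 days |

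**Share of the window.** A patient who stops on Day −14 could be scanned on the old drug on 14 of the 28 permitted days (Day −28 to Day −15), or one half. With a stop on Day −21 it is 28 − 21 = 7 days, or one quarter. With a stop on Day −28 or earlier it is none. These count permitted days, not how often it happens.

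**Spacing of the two scans.** At most 28 + 14 + 2 = 44 days.

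**Do other passages close the gap?**

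- Section 12.2.3 asks for baseline evaluations as near the start of treatment as possible, but still allows 4 weeks.
- Section 13.4 limits imaging obtained before consent to 14 days before treatment. A dual-energy CT done as a study procedure after consent keeps the 28 days.
- Section 5.1 requires imaging proof of progression after a course of standard treatment. That is an eligibility condition and does not date the dual-energy CT.

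None excludes an on-drug baseline scan.

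**Who could be affected.** Dual-energy CT is scheduled in the expansion (19 patients) and the pilot (10), so 19 + 10 = 29 is the ceiling. Only those coming from a VEGF-targeted TKI other than axitinib are exposed, and the documents do not give their number.

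**The case against.** The case on the other side is substantial.

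- **The scenario is narrow.** Section 12.2.3 pushes scans toward Day 1, and Section 13.4 rules out early scans taken before consent. An on-drug baseline therefore needs a patient with documented progression who consents, is scanned early and stays on the failing drug a little longer. This stands as a reason to expect few cases, but it does not exclude them.
- **Important prior drugs are not involved.** Bevacizumab plus interferon-alfa and prior axitinib have washouts long enough to prevent overlap. A last therapy with an mTOR inhibitor or immunotherapy may overlap in time, but the anti-angiogenic argument does not cover it. This stands and limits the point to other VEGF-targeted TKIs.
- **The bias is not quantified.** These patients have progressed, so little vascular suppression may be left to lose. This also stands. The direction rests on the plan's own expectation for axitinib, and no figure for withdrawal is given.
- **The analysis is peripheral.** Iodine density appears in neither list of objectives (Sections 1.0 and 14.2) and has no sample-size basis. This limits the consequence. It does not make the attribution in Section 21.4 sound.

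A reader might infer that half of the baseline scans were taken on drug, or that the imaging result is known to be biased toward SLM. The documents support neither: they show what is permitted, not what occurred.

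**Conclusion.** The concern holds for patients whose last therapy was a VEGF-targeted TKI other than axitinib. For them the plan permits a baseline dual-energy CT up to 14 days before the last dose and a visit 2 scan about 26 to 30 days after it, and Section 21.4 credits the change to SLM without a control. This assumes that the washout is counted to SLM Day 1. If a site counted it to an earlier date such as consent, the overlap would shrink or vanish. The direction of bias is inferred, and its size and the number of patients affected are unknown.

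The primary safety, dose and Day 14 selenium concentration endpoints are not affected. A reader might extend the point to RECIST response and PFS, since they use the same scan window. Growth between a baseline scan and Day 1 is a feature of any pre-treatment window, and it would count against the combination rather than for it, so it is not part of this finding. The point is worth correcting because the remedy is cheap, but it is confined to a correlative analysis.

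**What to change.** **Scan timing, for patients still to be scanned.** In footnote 7 and Sections 4.1.2 and 21.2, require the baseline dual-energy CT to be after the last dose of prior systemic therapy and within 28 days of SLM Day 1. The washout length stays as it is. The condition should refer to the last dose and not to completion of the washout, because a patient with the minimum 14-day gap completes it only at about Day 1. Expansion enrollment is complete, so this part can reach at most the 10-patient pilot.

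**Analysis, for all patients.** In Section 21.4, before the iodine data are examined:

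- Use the recorded stop and scan dates to report the visit 1 to visit 2 iodine change with and without patients whose baseline scan came before the last dose of a prior VEGF-pathway drug, or within a short interval after it that is fixed in advance.
- Show time since last dose beside each patient's result.
- Credit a rise to SLM only if it persists in patients scanned off the prior drug.

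**Cost.** No new data should be needed: prior treatment is taken in the screening history, item 10 cannot be checked without a stop date, and scans are dated. Some scans will be booked later in screening. The off-drug subset will be smaller and its estimate less precise. Some carry-over may remain, since a patient scanned soon after stopping is still moving further from the last dose by visit 2.
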